4.6.5. Clinical Laboratory Evaluation

Limits from the performing laboratory will be used to define low (L) and high (H). Descriptive summaries by treatment and by nominal visit will be provided for the baseline and postbaseline values as well as the change from baseline values. The associated descriptive will be presented in International System of Units and in conventional units.

For selected laboratory analyte measurements collected quantitatively, observed, and change from baseline values for each visit may be displayed in plots for participants who have both a baseline and at least 1 postbaseline planned measurement. Unplanned postbaseline measurements will be excluded from plots.

A shift table will be provided including unplanned measurements. The shift table will include the number and percentage of participants within each baseline category (low, normal, high, or missing) versus each postbaseline category (low, normal, high, or missing) by treatment. The proportion of participants shifted will be compared between treatments using Fisher's exact test.

For qualitative laboratory analytes, the number and percentage of participants with normal and abnormal values will be summarized by treatment.

A listing of abnormal findings will be created for laboratory analyte measurements, including qualitative measures. The listing will include:

- participant identification
- treatment group
- laboratory collection date
- study day
- analyte name, and
- analyte finding.

The MMRM model or ANCOVA (if MMRM model is not applicable) as described in Section 4.6 will be used for the analysis during the treatment period (excluding the safety follow-up period) for the continuous measurements for selected laboratory tests with or without log-transformed (postbaseline measure/baseline measure) response variables. For measures analyzed using log-transformed values, the results will be presented with the scale back transforming to the original, related scale.

The summary of treatment-emergent abnormal, high, or low laboratory results any time will be provided.

4.6.6. Product Complaints

A listing of all product complaints by subcategory, inclusive of device product complaints that led to an AE or that could have led to an SAE had intervention not been taken, will be provided.

4.7. Other Analyses

4.7.1. PAP Adherence

For participants in ISA2 only, the adherence to use of the PAP machine over the course of the study will be summarized. Specifically, the summary statistics for PAP adherence at baseline and at each postbaseline week, stratified by treatment arm will be provided. Additionally, the categorical shift in PAP adherence between baseline and Week 52, stratified by treatment arm using a shift table for increased, decreased, or stable PAP use will be assessed. Finally, the number and percentage of participants in ISA2 who withdraw from regular PAP use will be summarized.

4.7.2. Health Outcomes

The PRO questionnaires will be analyzed using the mITT population on the EAS, unless specified otherwise.

Item-level missingness will be dealt with per the instrument developers' instruction.

Additional psychometric analyses will be performed by Value, Evidence, and Outcomes at Lilly and documented in a separate analysis plan.

Analyses of actual and change from baseline in PRO scores will be conducted using linear models with baseline PRO scores, treatment, stratification factors, and other factors that may be considered relevant.

If an administrative error occurs where more than 1 PRO questionnaire is completed within the same visit window by the same participant with different responses on at least 1 item, the questionnaire with the worst response will be used (for example, the questionnaire with the highest PHQ-9 score will be used). If more than 1 PRO questionnaire is completed within the same visit window with the same response to each item, the most recent response will be used.

4.7.2.1. Functional Outcomes of Sleep Questionnaire

The FOSQ will be included to assess change in FOSQ domains and total score from baseline to Week 52. The FOSQ is a 30-item sleep-specific, participant-completed questionnaire used to assess the effect of disorders associated with excessive daytime sleepiness on daily functioning in adults. It assesses the following 5 domains of:

- General productivity (8 items)
- Activity level (9 items)
- Vigilance (7 items)
- Social outcomes (2 items), and
- Intimate and sexual relationships (4 items).

The FOSQ items assess participant's current status with each item rated on a scale of 1 (extreme difficulty) to 4 (no difficulty), with an additional not applicable (0 = "I don't do this activity for other reasons") also available. Individual domain scores are calculated by taking the mean of answered, non-zero items within each domain and ranges from 1 to 4 with higher scores indicating better outcomes. A total score can be calculated by first computing the mean score for each domain, then multiplying the mean of the domain scores by 5 (Weaver et al. 1997). The change from baseline in all 5 FOSQ domain scores will be assessed.

4.7.2.2. Functional Outcomes of Sleep Questionnaire, 10 Items

The FOSQ-10 will be included to assess change in FOSQ total score domains from baseline to Week 52. The 10-item sleep-specific, participant-completed questionnaire is a shortened version of the FOSQ with the same number of domains as the parent version. Of note, the FOSQ-10 has the same 5 domains as the FOSQ, but with fewer items per domain.

Calculation of the individual domain scores and the total score for the FOSQ-10 is carried out in a similar manner to FOSQ. The domain scores are first calculated by taking the mean of the answered, non-zero items within each domain. The total score is calculated by multiplying the mean of the domain scores by 5 (for each domain which has at least 1 response).

4.7.2.3. Epworth Sleepiness Scale

The ESS is an 8-item participant-completed measure that asks the participant to rate on a scale of 0 (would never doze) to 3 (high chance of dozing), their usual chances of dozing in 8 different daytime situations, with a recall period of “in recent times.” The ESS total score is the sum of the 8-item scores and ranges from 0 to 24, with higher scores indicating greater daytime sleepiness (Johns 1991). Of note, if 1 or more item scores are missing, the ESS total score is not valid and will not be included in the analysis.

4.7.2.4. PROMIS Short Form v1.0 Sleep-Related Impairment 8a

The PROMIS Short Form v1.0 Sleep-Related Impairment 8a consists of 8 items each rated on a 5-point scale ranging from “not at all” to “very much.” Items have a recall period of “in the past 7 days.” Individual item scores will be combined and converted to a T-score using a response pattern scoring approach (Northwestern 2016a). The T-score standardizes the raw score to a distribution with a mean of 50 and standard deviation of 10.

4.7.2.5. PROMIS Short Form v1.0 Sleep Disturbance 8b

The PROMIS Short Form v1.0 Sleep Disturbance 8b consists of 8 items each rated on a 5-point scale ranging from “not at all” to “very much,” “never” to “always,” or “very poor” to “very good.” Items have a recall period of “in the past 7 days.” Individual item scores will be combined and converted to a T-score using a response pattern scoring approach (Northwestern 2016b). The T-score standardizes the raw score to a distribution with a mean of 50 and standard deviation of 10.

For item 8 of this scale (which is a measure of sleep quality), counts and percentages of participants at each time point will be summarized by nominal visit and by treatment. A shift table from baseline to postbaseline will be created at each postbaseline visit.

4.7.2.6. Short-Form-36 Health Survey Version 2, Acute Form

Per copyright owner, the QualityMetric Health Outcomes™ Scoring (PRO_CoRe V2.0) Software will be used to derive the following domain and component scores:

- Mental Component Score (MCS)
- Physical Component Score (PCS)
- Physical Functioning domain (PF)
- Role-Physical domain (RP)
- Bodily Pain domain (BP)
- General Health domain (GH)
- Vitality domain (VT)
- Social Functioning domain (SF)
- Role-Emotional domain (RE), and
- Mental Health domain (MH).

The following analyses for the actual value and change from baseline value for each domain and component score will be conducted:

- descriptive summaries by treatment group, and
- analysis described in [Table GPIF.4.3](#).

4.7.2.7. Patient Global Impression of Status/Change for OSA Outcomes

The counts and percentages of participants for PGIS for Physical Activity and PGIC response categories at each time point will be summarized by nominal visit and by treatment. A shift table from baseline to postbaseline of 3 PGIS response categories (OSA Sleepiness, Fatigue, and Snoring) and 4 PGIC response categories (OSA Sleepiness, Fatigue, Snoring, and Sleep Quality) will be created at each postbaseline visit.

4.7.2.8. EQ-5D-5L

For the utility score and the Visual Analog Scale scores, the following analyses of the actual value and change from baseline value will be conducted:

- descriptive summaries by treatment group, and
- ANCOVA described in [Table GPIF.4.4](#).

4.7.3. Subgroup Analyses

The following subgroups will be analyzed using the efficacy estimand on change in AHI values from baseline to 52-week visit if there is an adequate number of participants in each treatment by subgroup (for example, 10%):

- age (<50 years, \geq 50 years)
- baseline OSA severity (not severe, severe)
- race
- ethnicity
- region of enrollment (US, OUS)
- gender (male or female)
- baseline BMI (<35, \geq 35 and <40, \geq 40 kg/m²), and
- baseline ESS (ESS \leq 10, ESS $>$ 10).

Analyses for change from baseline in AHI will be performed using an MMRM model that includes the same fixed effects given for the primary analysis model plus factors of subgroup, 2-way interaction of subgroup and treatment, 2-way interaction of subgroup and visit, and 3-way interaction of treatment, visit, and subgroup. The possible interaction effect of subgroup and treatment at the primary endpoint (Week 52) will be evaluated. When analyzing OSA severity (not severe, severe) as a subgroup, the baseline AHI will not be included as a covariate to avoid confounding.

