#### 9.3.7.2. Subgroup Analyses

The following subgroups will be analyzed using the “efficacy” estimand on percent change in AHI values from baseline to 52 week visit if there are sufficient numbers of participants in each treatment by subgroup (for example, 10%):

- Age (<50 years,  $\geq$ 50 years),
- Baseline OSA severity (Moderate, Severe),
- Race,
- Ethnicity,
- Country,
- Gender (Male or Female),
- Baseline BMI (<30,  $\geq$ 30 and <35,  $\geq$ 35 and <40,  $\geq$ 40 kg/m^2), and
- Baseline ESS (ESS $\leq$ 10, ESS $>$ 10).

Analyses for percent change from baseline in AHI will be performed using an MMRM model that includes the same fixed effects given for the primary analysis model plus factors of subgroup, 2-way interaction of subgroup and treatment, 2-way interaction of subgroup and visit, and 3-way interaction of treatment, visit and subgroup. The interaction of subgroup and treatment at the primary endpoint (Week 52) will be evaluated to assess the treatment by subgroup interaction. When analyzing OSA severity (Moderate, Severe) as a subgroup, the baseline AHI will not be included as a covariate to avoid confounding. Additional subgroup analyses may also be performed.

More details on other analyses will be described in the SAP.

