Statistical treatment comparisons will be performed between tirzepatide MTD and placebo. Unless otherwise noted, all tests of treatment effects will be conducted at a 2-sided alpha level of 0.05, and the confidence interval will be calculated at a 2-sided 95% level. In statistical summaries and analyses, participants will be analyzed as randomized. Analysis models will use geographic region (US/OUS) as a covariate when applicable.

Analysis of covariance will be used to analyze continuous variables collected only at baseline and endpoint. Unless otherwise specified, the model will include treatment and strata (geographic region [US/OUS], AHI stratum [not severe (AHI <30), severe (AHI \geq 30)], and gender) as fixed effects and baseline as a covariate.

MMRMs will be used to analyze continuous variables collected at baseline and more than 1 postbaseline visit. For the MMRM analysis, REML will be used to obtain model parameter estimates for continuous longitudinal variables. All the longitudinal observations at each scheduled postbaseline visit will be included in the analysis. The model will include the fixed class effects of treatment, strata (geographic region [US/OUS] and gender), visit, and treatment-by-visit interaction, as well as the continuous, fixed covariate of baseline value. For analyses of variables other than AHI, the AHI stratum will also be included in the model. Significance tests will be based on least squares means and Type III tests.

For continuous measures, summary statistics may include sample size, mean, standard deviation, median, minimum, and maximum for both the actual and the change from baseline measurements. Least-square means and standard errors derived from the analysis models will also be displayed for the change from baseline measurements. Treatment comparisons will be displayed showing the treatment difference least-square means and the 95% confidence intervals for the treatment differences, along with the p-values for the treatment comparisons.

For categorical measures, summary statistics may include sample size, frequency, and percentages. Fisher's exact test or Pearson's chi-square test will be used for treatment comparisons unless otherwise specified.

Not all analyses described in this SAP will necessarily be included in the CSRs. Any analysis described in this SAP and not provided in the CSR would be available upon request.

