4.1.1. Adjustment for Covariates

The study is stratified by country/geographic region, OSA severity (not severe [AHI <30], severe [AHI \geq 30]), and gender. Unless otherwise specified, the following factors will be adjusted for: geographic region (US/OUS), OSA severity (not severe [AHI <30], severe [AHI \geq 30]), and gender. The value for stratification factors will be obtained from the data collected or derived from the eCRF or PSG results. In addition, the baseline value of the endpoint will be used as a covariate when appropriate.

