4.3.1. Analysis Related to the Efficacy Estimand

The primary analysis guided by the "efficacy" estimand will be conducted using the EAS. This analysis will be based on the contrast between tirzepatide at the MTD (10 mg or 15 mg) and placebo at Week 52 (Visit 11) from the MMRM analysis of mean change from baseline in AHI. All the longitudinal observations at each scheduled postbaseline visit will be included in the analysis. REML will be used to obtain model parameter estimates and the Kenward-Roger option will be used to estimate the denominator degrees of freedom. The response variable of the MMRM will be the change in AHI from baseline values obtained at each scheduled postbaseline AHI measurement.

The model will include the fixed class effects of treatment, strata (geographic region [US/OUS] and gender), visit, and treatment-by-visit interaction, as well as the continuous, fixed covariate of baseline AHI. An unstructured covariance structure will be used to model the within-participant errors. Significance tests will be based on least squares means and Type III tests. If this analysis fails to converge, the following covariance structures will be tested in order until convergence is achieved:

- Toeplitz with heterogeneity
- autoregressive with heterogeneity
- compound symmetry with heterogeneous variances
- Toeplitz
- autoregressive, and
- compound symmetry without heterogeneous variances.

Analysis aligned to each estimand will be evaluated at the full significance level of 0.05.

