4.4.1.1. Main Analytical Approaches

Analysis of percent change in AHI, percent change from baseline to Week 52 in body weight, change from baseline to Week 52 in log of high-sensitivity C-reactive protein, change from baseline to Week 48 in SBP, change from baseline to Week 52 in PROMIS Sleep-related impairment, change from baseline to Week 52 in PROMIS Sleep disturbance, and change from baseline to Week 52 in log of hypoxic burden will be conducted in a manner similar to the primary efficacy analyses using an ANCOVA model with treatment, strata (geographic region [US/OUS], AHI stratum [not severe (AHI <30), severe (AHI \geq 30)], and gender), and baseline of the corresponding variable as a covariate for the treatment regimen estimand. If the hypoxic burden is reported to be 0, log (1) will be used in place of the log of hypoxic burden. The analysis method utilizing data from both ISAs for change from baseline to Week 52 in PROMIS sleep Impairment and PROMIS Sleep disturbance is described in the integrated efficacy analysis plan.

For the efficacy estimand, the MMRM analyses will be conducted as described in Section 4.1. For both estimands, analysis of percent change in AHI will adjust for the continuous, fixed baseline value of AHI instead of the baseline AHI stratum (not severe, severe).

Comparisons at the 52-week visit between the treatments relative to the proportion of participants achieving \geq 50% AHI reduction and AHI <5 or (AHI 5 through 14 and ESS \leq 10) will be conducted using logistic regression analysis including the following terms as a covariate:

- treatment
- geographic region (US/OUS)
- baseline AHI, and
- gender.

Unconditional risk differences will also be provided for these endpoints using logistic regression (Ye et al. 2023).

Analysis aligned to each estimand will be evaluated at the full significance level of 0.05 contingent on reaching statistical significance of the primary objective.

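### The OSA-severity subgroup model drops baseline AHI on a confounding argument that does not apply, at a small avoidable cost in precision

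*SAP*

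**What the plan says.** SAP section 4.7.3 takes the primary efficacy-estimand MMRM for change in AHI and adds the subgroup factor with "2-way interaction of subgroup and treatment, 2-way interaction of subgroup and visit, and 3-way interaction of treatment, visit, and subgroup". The primary model's terms include "treatment-by-visit interaction, as well as the continuous, fixed covariate of baseline AHI" (SAP section 4.3.1), so the other subgroup models inherit baseline AHI. Severity is the single exception: there "the baseline AHI will not be included as a covariate to avoid confounding".

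Protocol section 9.3.7.2 has the same rule and the same reason: "When analyzing OSA severity (Moderate, Severe) as a subgroup, the baseline AHI will not be included as a covariate". Its subgroup outcome is percent change in AHI, whereas the SAP's is absolute change.

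The severity grouping is baseline AHI cut at 30, and it is also a randomisation factor (Protocol section 6.3). SAP section 4.1.1 puts it this way: "The study is stratified by country/geographic region, OSA severity (not severe [AHI <30".

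Neither document gives the correlation between baseline AHI and its change, the expected share of severe participants, or a target precision for any subgroup.

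**The concern.** A covariate confounds a treatment comparison when it is associated with treatment assignment. Randomisation within severity strata removes that association by design, so the stated reason does not apply to the treatment difference or to its interaction with severity, which is what section 4.7.3 sets out to evaluate.

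Dropping the covariate may also cost something. The severe group has no upper AHI limit, and the SAP analyses absolute change. If the effect is roughly proportional, change depends on the starting value. The sample-size section plans on a 50% improvement: a 50% fall is 0.5 × 35 = 17.5 events/h from a baseline of 35, and 0.5 × 90 = 45 from a baseline of 90. Both participants are severe. The severity factor absorbs differences between the two groups but not this spread within one. At stake is the precision of a subgroup result that readers are likely to look at.

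**Working it through.** **The plan's own figure.** The only precision figure for AHI is at least 90% power for percent change in a whole ISA. With 103 × 0.75 = 77 evaluable per arm, difference 50, SD 50 and two-sided alpha 0.05, power is 99.999%; 90% needs 22 per arm, or 30 after 25% dropout. The statement holds, but it says nothing about subgroup precision.

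**Bias.** A Week 52 linear model stood in for the MMRM contrast: 154 evaluable, randomisation stratified by severity, terms for treatment, severity, their interaction, gender and region. Assumed inputs were 65% severe, a gamma-shaped AHI above 30 and residual SD 15. With a true effect of −20 in both groups and a within-group correlation rho of 0.4, the estimates were −19.95 (not severe) and −20.12 (severe) without baseline, and −19.95 and −20.11 with it. Neither model is biased.

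**Size from a formula.** If the residual SD were specific to the group, omitting a covariate with within-group correlation rho would widen the interval by the factor 1/√(1 − rho²):

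- rho 0: none
- rho 0.2: 1/√0.96 = 1.02
- rho 0.4: 1/√0.84 = 1.09
- rho 0.6: 1/√0.64 = 1.25

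**Size from simulation, severe group, SE ratio omitted/kept.** Empirical means the actual sampling SD of the estimate; model means the reported SE under one residual variance pooled over groups.

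| Assumed setting | Model | Empirical |
|---|---|---|
| Additive, rho 0 | 0.995 | 0.996 |
| Additive, rho 0.2 | 1.009 | 1.009 |
| Additive, rho 0.4 | 1.057 | 1.077 |
| Additive, rho 0.6 | 1.168 | 1.251 |
| Proportional, 50% v 0%, residual SD 10 | 1.065 | 1.092 |
| Same, residual SD 15 | 1.028 | 1.049 |
| Same, residual SD 20 | 1.016 | 1.021 |

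A further run used 206 participants, lognormal baseline (median 45, range 15 to 150), 10% v 50% reduction and residual SD 14 to 18. The severe-group empirical SE fell from 2.53 to 2.30 (ratio 1.10) and from 3.09 to 2.89 (ratio 1.07) when centred baseline was kept. A separate run of this kind cut the variance by 9 to 17% at residual SD 14 to 18 and by 4 to 7% at SD 25. As width ratios these are 1/√0.91 = 1.05 to 1/√0.83 = 1.10, and 1/√0.96 = 1.02 to 1/√0.93 = 1.04. Hence the range of roughly 2 to 10%.

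**Interaction.** The empirical SD of the treatment-by-severity contrast, omitted v kept, was 5.02 v 4.84 (ratio 1.04) and 6.32 v 6.16 (1.03) in lognormal runs, and the ratio was 1.01 to 1.04 in the proportional runs. It reached 1.10 only in the additive run at rho 0.6.

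**What omission protects.** Adding uncentred baseline AHI beside its own dichotomy raises the SE of the severity main effect from 3.60 to 4.53 at rho 0 (+26%) and from 3.82 to 4.53 at rho 0.4 (+19%). It also changes what that effect means: at rho 0.4 it moves from −11.7 to about 0, because both groups are then judged at a common AHI. Centring within group avoids this. A shift by a constant per group is absorbed by the severity terms, so the treatment contrasts are the same as with uncentred baseline, while the main effect and LS means refer to each group's own mean.

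**The case against.** The rule is prespecified in both documents and resembles the plan's habit of using one form of baseline AHI: "analysis of percent change in AHI will adjust for the continuous, fixed baseline value of AHI instead of the baseline AHI stratum" (SAP section 4.4.1.1). That is a fair description, but the habit elsewhere keeps the continuous form and drops the stratum. Here severity must stay because it is the subgroup, so the convention does not settle the matter.

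Omission also has a genuine rationale: uncentred baseline would distort the severity main effect and put both groups' LS means at an AHI that may suit neither. That stands as a reason for centring, not as a reason to omit, and it is not confounding.

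It is also right that the size cannot be derived from the documents, that the severity factor retains the between-group part of baseline AHI, and that chance baseline imbalance is not a second loss: it is the mechanism of the same one and is already in the standard error.

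Four stronger readings are tempting and should not be drawn.

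- **That baseline AHI is the strongest covariate available.** The documents do not rank covariates.
- **That severity would be estimated less precisely than every other subgroup.** Group size matters more. With lognormal inputs that put about 79% in the severe group and residual SD 14, the severe-group SE without baseline is 2.52, against 3.63 for a one-third BMI band and 4.74 for a 20% subgroup, both with baseline.
- **That only the severe interval widens.** The SAP states that "An unstructured covariance structure will be used to model the within-participant errors" and gives no separate covariance by subgroup. Reported intervals then widen about equally in both groups (1.06 and 1.06 at rho 0.4), although the added sampling noise falls mainly in the severe group (1.08 v 1.01).
- **That the interaction test is compromised.** It changes little.

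**Conclusion.** The rationale is wrong and the modelling choice gives away a little precision. There is no confounding of the treatment effect to avoid, and omission brings no gain for the treatment differences or the interaction. It leaves the subgroup effects unbiased, with a severe-group interval wider by roughly 2 to 10%.

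That range rests on assumed inputs: the baseline distribution, the share of severe participants, the residual SD, and a within-group dependence of change on baseline. With no such dependence the loss is nil; at a within-group correlation of 0.6 it would be 17 to 25%. The calculations use a Week 52 linear model rather than the full MMRM.

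A reader might infer that the severity results would be invalid or that a main conclusion is at risk. The documents do not support that. SAP section 2.1 limits multiplicity control to the primary and key secondary objectives, the subgroup analysis lies outside them, and none of those tests uses this model. The point is minor.

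**What to change.** In SAP section 4.7.3, delete the confounding rationale and keep continuous baseline AHI in the severity subgroup MMRM, centred within each severity group, with LS means taken at each group's own mean. If the sponsor prefers to leave the specified model as the main one, the centred model can be prespecified as supportive and the reason for omission reworded as collinearity with the severity main effect. Protocol section 9.3.7.2 carries the same sentence; the departure can be recorded in the SAP's list of changes to protocol-planned analyses. The cost is one sentence and one model term, with no new data.
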